#### **7.8.4 ECG**

Abnormal findings will be reported as baseline conditions (prior to first study drug administration) or as AEs (from first study drug administration onwards) if judged clinically relevant by the investigator.

The ECG exposure response analysis will be based on the ECGPCS. All other descriptive analysis of ECG endpoints will be based on the TS.

Generally, ECG measurements will not be included in the statistical analysis if one of the following applies:

- No date or time available for ECG measurement
- Pre-dose measurement done after first drug administration
- On-treatment measurement done before first drug administration
- Measurement is a repeated measurement
- More than 3 single ECGs (i.e., measurements from 4th single ECG onwards will not be included)
- Unscheduled measurements

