5.2.4 Electrocardiogram

Recording and storing

Twelve-lead ECGs (I, II, III, aVR, aVL, aVF, V1 - V6) will be recorded using a computerised electrocardiograph (e.g. Mortara Eli 250 C) at the times provided in the [Flow Chart](#).

To achieve a stable heart rate at rest and to assure high quality recordings, the site personnel will be instructed to assure a relaxed and quiet environment, so that all subjects are at complete rest.

All ECGs will be recorded for a 10 sec duration after subjects have rested for at least 5 min in a supine position. ECG assessment will always precede all other study procedures scheduled for the same time to avoid compromising ECG quality.

ECGs will be recorded as single ECGs or as triplicate ECGs (i.e. three single ECGs recorded within 180 sec) as indicated in the [Flow Chart](#).

All ECGs will be stored electronically. Electrode placement will be performed according to the method of Wilson, Goldberger and Einthoven.

All locally printed ECGs will be evaluated by the investigator or a designee. Abnormal findings will be reported as AEs (during the trial) or baseline conditions (at screening) if assessed to be clinically relevant by the investigator. Any ECG abnormalities will be carefully monitored and, if necessary, the subject will be removed from the trial and will receive the appropriate medical treatment.

ECGs may be repeated for quality reasons (for instance, due to alternating current artefacts, muscle movements, or electrode dislocation) and the repeated ECG will be used for analysis. Additional (unscheduled) ECGs may be collected by the investigator for safety reasons.

Data transfer

In case of repeat ECGs due to quality reasons, all recordings will be transferred to the central ECG lab and the repeated ECGs will be flagged in the database.

Unscheduled ECGs (for safety reasons) will be transferred to the central ECG lab and evaluated but will not be included into the statistical analysis of interval lengths. Data transfer from the central ECG lab to the sponsor is described in the ECG data transfer agreement (see TMF).

Evaluation by the central ECG laboratory

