Adverse events will be coded using the Medical Dictionary for Regulatory Activities (MedDRA). Frequency, severity, and causal relationship of AEs will be tabulated by treatment, system organ class, and preferred term. SAEs, AESIs (see Section [5.2.6.1](#)), and other significant AEs (according to ICH E3) will be listed separately.

Previous and concomitant therapies will be presented per treatment group without consideration of time intervals and treatment periods.

Laboratory data will be compared to their reference ranges. Values outside the reference range as well as values defined as possibly clinically significant will be highlighted in the listings. Additionally, differences from baseline will be evaluated.

Vital signs or other safety-relevant data will be assessed with regard to possible on-treatment changes from baseline.

Relevant ECG findings will be reported as AEs.

A centralised evaluation of all 12-lead ECGs recordings (see Section [5.2.4](#)) will be the basis for the derivation of further qualitative and quantitative ECG endpoints, including the calculation of heart rate corrected QT intervals. The TSAP will provide further details.

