#### **4. CHANGES IN THE PLANNED ANALYSIS OF THE STUDY**

All analyses described in this TSAP are in accordance with the statistical methods planned in the revised CTP.

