## 6.7 BASELINE, TIME WINDOWS AND CALCULATED VISITS

A separate baseline is defined for each treatment period: Baseline is the last available off-treatment value before administration of the respective treatment (BI, BI fasted, BI fed). Off-treatment in this context means that a value measured within an on-treatment phase, as defined in [Table 6.1: 1](#), will not be used as baseline for any study treatment.

There will be a centralised evaluation of 12-lead ECG recordings at the time points specified in [Table 6.7: 1](#).

Three triplicate ECGs will be recorded as the baseline before the each oral drug administration, but only all 3 single ECGs of the first of the 3 triplicates will be transferred to the database. Triple ECGs (3 single ECGs recorded within 180 sec) will be recorded on all on-treatment time points with centralised ECG evaluation.

The baseline value of an ECG variable is defined as the mean of the triple ECG measurements prior to first study drug administration. For all on-treatment assessments, only the first of the three replicate ECG at a single assessment time will be centrally evaluated.

Table 6.7: 1 Time schedule of 12-lead ECG recordings with centralised evaluation

Visit	Day	Planned time [hh:mm] - relative to respective drug administration	Study phase
2/3/4	1	-01:00	Baseline On-treatment
		01:00	
		04:00	
		08:00 	
		12:00	
	2	24:00	

 in Part 1 only

For the exposure response analyses, pairs of ECG variables and corresponding plasma concentrations will be built using the same planned time points, e.g., the HR change from baseline and the plasma concentration measured at planned time 01:00 will build one pair. Whether a time deviation between PK blood sampling time and corresponding ECG recording is too big for a reliable assessment and the pair has to be excluded from the analysis will be decided no later than at the RPM.

Time windows are defined in Section 6.1 of the CTP. Adherence to time windows will be checked at the RPM.

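### The SAP drops every repeated ECG, while the protocol says an ECG repeated for quality reasons is the one to analyse

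*SAP*

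**What the plan says.** Protocol 5.2.4 distinguishes two kinds of extra ECG and treats them in opposite ways.

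- **Repeated for quality reasons** (for example artefact, muscle movement or a displaced electrode): the repeat replaces the original, "and the repeated ECG will be used for analysis". For these cases "all recordings will be transferred to the central ECG lab and the repeated ECGs will be flagged in the database".
- **Unscheduled, taken for safety**: sent to the central laboratory, "evaluated but will not be included into the statistical analysis of interval lengths".

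Protocol 7.3.4 refers to Section 5.2.4 and says the centralised evaluation "will be the basis for the derivation of further qualitative and quantitative ECG endpoints".

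SAP 7.8.4 lists conditions under which an ECG is generally left out of the statistical analysis. Three of them matter here, each in its own bullet: "Measurement is a repeated measurement"; more than three single ECGs, where "measurements from 4th single ECG onwards will not be included"; and unscheduled measurements.

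SAP 6.7 adds that on treatment "only the first of the three replicate ECG at a single assessment time will be centrally evaluated". SAP 6.6 rules out imputation of ECG endpoints. SAP 4 states: "All analyses described in this TSAP are in accordance with the statistical methods planned in the revised CTP".

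**The concern.** For the same tracing, the protocol says to use it and the SAP says to leave it out. The SAP keeps the protocol's rule for unscheduled safety ECGs but reverses the rule for quality repeats, and does not declare this as a change.

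A programmer would probably apply the bullet through the database flag. Under the protocol that flag marks the repeat, so filtering on it removes the good tracing. What remains is either the original that was judged inadequate or no value at all.

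At stake are the outputs of SAP 7.8.4: the change-from-baseline tables and profiles, the notable-finding tables and listing, the QTcF and heart-rate exposure-response plots, and the check of the heart-rate correction. A single bad tracing matters most where individual values are shown.

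**Working it through.** **Comparing the rules**

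| Type of ECG | Protocol 5.2.4 | SAP 7.8.4 |
|---|---|---|
| Unscheduled, for safety | excluded from interval analysis | excluded (own bullet) |
| Fourth single ECG onwards | no rule stated | excluded (own bullet) |
| Repeated for quality reasons | the repeat is analysed | excluded (own bullet, no exception) |

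Unscheduled recordings and surplus singles have their own bullets, so the repeated-measurement bullet cannot be explained as covering only those. It must add something, and quality repeats are the class of repeat that the protocol defines.

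The fourth-single rule makes this worse. If one ECG of a triplicate is redone, the repeat can be the fourth single at that time point. Correcting only the repeated-measurement bullet could then leave it excluded by the other.

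**How many values could be involved**

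Inputs: the time points in SAP Table 6.7: 1, 12 planned subjects (protocol 7.7), three single ECGs per baseline (SAP 6.7), and a separate baseline for each of three periods (SAP 6.7).

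- On-treatment time points per subject: Part 1 has 5 (1, 4, 8, 12 and 24 h). Part 2 has 4 (1, 4, 12 and 24 h) in each of 2 periods, so 8. Total 5 + 8 = 13.
- On-treatment values, each from one ECG: 13 × 12 = 156.
- Baseline single ECGs: 3 × 3 × 12 = 108.

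These are totals of planned tracings. The number actually affected lies between 0 and 156 on treatment and between 0 and 108 at baseline. The documents give no repeat rate to narrow this.

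**Effect of one tracing**

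Suppose a poor original is retained and its QTcF is wrong by *d* ms.

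- On treatment, that subject's change from baseline is wrong by *d*, and the time-point mean by *d* × 1/12 = 0.083*d*.
- At baseline, the subject's baseline is wrong by *d*/3, and each time-point mean change by (1/3) × (1/12) × *d* = *d*/36 = 0.028*d*, in the opposite direction. This recurs at every on-treatment time of that period: 5 in Part 1, 4 in each Part 2 period.

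If the value is lost instead:

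- On treatment, n falls from 12 to 11. With the standard deviation unchanged, the standard error rises by √(12/11) = 1.044, about 4%.
- At baseline, the subject's value becomes the mean of 2 tracings instead of 3.

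**The case against.** The best counter-argument is that the bullet may mean something narrower. SAP 7.8.2 and 7.8.3 use the term repeat measurement for readings taken to confirm a value. If the ECG bullet meant confirmatory repeats, it would leave a gap beside the protocol, not contradict it. It could also have meant the superseded original, which would agree with the protocol. Neither limit is in the bullet. The first would largely duplicate the bullet on unscheduled measurements. The second goes against the usage of protocol 5.2.4 and of SAP 7.8.2 and 7.8.3, where the repeat is the later reading. Even if one of them was intended, the wording has to change, because the database flag identifies the repeat.

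It can also be said that SAP 4 vouches only for statistical methods, that SAP 3 ties the SAP chiefly to protocol Section 7, and that protocol 7.3.4 leaves ECG detail to the SAP. But protocol 7.3.4 itself refers to Section 5.2.4 for the central evaluation. Leaving detail to the SAP does not cover an undeclared reversal.

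Other safeguards exist: fallback to another lead, cardiologist review, averaging over available beats, stored second and third replicates, and decisions on discrepant values at the Report Planning Meeting. The word *generally* also leaves some latitude. None of these restores the rule that the repeat is analysed.

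Two points stand. First, the Part 1 flow chart, as extracted, also marks a triplicate ECG for external evaluation at 10 h. Counting it gives 14 × 12 = 168 on-treatment values, and replacement subjects could raise the total further. SAP Table 6.7: 1 governs what is analysed, so 156 is the count used here, and the conclusion does not depend on it. Second, the impact is modest: cardiac safety during the study is judged on site QT and QTcB values, and clinically relevant findings are reported as adverse events in any case.

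**Conclusion.** The contradiction is real and should be corrected. On its plain reading, SAP 7.8.4 excludes the recording that protocol 5.2.4 selects, and SAP 4 does not disclose this.

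The consequence is confined to the descriptive and exposure-response ECG safety analyses. The primary and secondary pharmacokinetic endpoints are not affected. For means the effect of a single tracing is small, as shown above. For an individual's notable finding or point on an exposure-response plot, it can be the whole value.

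This rests on three assumptions: the bullet means what it says; no exception sits in text that is not visible; and 12 subjects complete all periods, with the standard deviation unchanged if a value is lost.

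**What to change.** In SAP 7.8.4, replace the bullet with: *The original recording, where it was repeated for quality reasons; the repeat takes its place (CTP Section 5.2.4).*

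State the order of operations: this replacement is made before the rule on the fourth single ECG, before the first on-treatment replicate is selected, and before the baseline triplicate is averaged.

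If the sponsor does intend to exclude quality repeats, SAP 4 should declare the departure from the protocol and justify it.

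Two separate editorial points in the SAP's ECG text can be tidied at the same time. The reference to renal function groups in SAP 7.8.4 should name this trial's treatments. References to the first drug administration should match the per-period baseline defined in SAP 6.7.

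The cost is SAP wording. All recordings already go to the central laboratory with repeats flagged, so at most the laboratory reads a tracing it already holds. The sponsor should confirm that the ECG data transfer agreement, which is not part of these documents, passes the repeat's interval values on to the analysis database.

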##### **Listing of individual data**

For all quantitative endpoints, listings of individual data will be shown in Appendix 16.2. For QTcB and RR, only listings will be provided. Occurrences of notable findings will be flagged.

Comments regarding the ECGs will be listed.

##### **Categorical endpoints**

For the categorical endpoints, frequency tables will be provided.

For all subjects with any notable finding in ECG intervals, a separate listing will be created as end-of-text display (based on the same display template as in Appendix 16.2), and the corresponding time profiles will be shown.

##### **Quantitative endpoints**

Descriptive statistics (N, mean, SD, min, median, max) will be provided for the changes from baseline over time of QTcF, HR, QT, PR and QRS. The time profiles of mean and SD for the changes from baseline on treatment will be displayed graphically by renal function group.

##### **Exposure-response assessment**

To assess the relationship between changes from baseline in QTcF and HR and the time-matched plasma concentrations of each subject group, several plots will be provided. For a list

of time points with scheduled ECG assessments and a time-matched plasma concentration, refer to [Table 6.7: 1](#).

For the handling of missing values, see [Section 6.6](#).

The remaining section describes the analysis for QTcF only, however the same plots will be performed for HR.

To investigate if there is a potential delayed or accelerated (e.g. due to metabolites) effect of the drug on QTcF, a general visual impression will be provided by overlaying time profiles of plasma concentrations and QTcF changes from baseline. These figures will be generated for each subject (presented in the Statistical Appendix of the CTR), as well as for means per subject group (presented in the End-of-Text part of the CTR).

For a visual inspection of the relationship between BI 1358894 plasma concentration and QTcF changes from baseline, a scatterplot of the individual values of BI 1358894 plasma concentration against QTcF changes from baseline will be created with separate symbols for each subject group. For QTcF a horizontal reference line at 60 msec will be added. Vertical lines at the gMean of  $C_{max}$  of the respective subject group will also be added.

#### Appropriateness of heart rate correction methods of QT interval

To evaluate the appropriateness of the heart rate correction methods, the slope of the relationship of QTcF interval versus RR interval (values log-transformed using the natural logarithm) will be estimated by applying a random coefficient model using all time points. A scatterplot of  $\ln(\text{QTcF})$  vs  $\ln(\text{RR})$  including the overall regression line will be included in the Statistical Appendix of the CTR. The resulting (fixed effect) slope together with two-sided 95% confidence intervals will be included in the footnote for this plot.

#### **7.8.5      Others**

##### Suicidality assessment

Suicidality monitoring will be performed as described in Section 5.2.5.1 of the CTP, results will only be listed. No further analysis will be prepared. Findings will also be reported as AEs.

##### Physical and neurological examinations

Physical and neurological examination findings will be reported as relevant medical history/baseline condition (if a condition already exists before first administration of study treatment) or as AE (if condition emerges after first administration of study treatment) and will be summarized as such. No separate listing or analysis of physical or neurological examination findings will be prepared.

## 9. ADDITIONAL SECTIONS

### 9.1 DETAILED DESCRIPTION OF ENDPOINTS FOR ECG

QT, PR, QRS and RR baseline and on-treatment measurements (see [Table 6.7: 1](#)) are included in the centralised ECG evaluation.

For each single ECG, measurements of QT, PR, QRS and preceding RR interval of four cardiac cycles will be determined and stored in the database as raw data. Their mean values will be used as the QT, PR, QRS, and RR interval values, respectively, for this ECG.

QTcF, HR and QTcB will be calculated based on the derivation rules as follows:

From the four cardiac cycles of a single ECG, the HR (measured in beats per minute, beats/min) will be calculated as

$$HR [beats/min] = \frac{60\,000}{\overline{RR}}$$

where  $\overline{RR}$  is the mean of the four RR intervals (measured in msec).

Similarly, the QT interval corrected for HR according to Fridericia's formula (QTcF) for a single ECG will be derived as

$$\overline{QTcF} [msec] = \left( \frac{1000}{\overline{RR}} \right)^{1/3} * \overline{QT} [msec],$$

where  $\overline{QT}$  is the mean of the four QT intervals and  $\overline{RR}$  is the mean of the corresponding preceding RR intervals of the four cardiac cycles for this ECG.

Likewise, the HR-corrected QT interval according to Bazett's formula (QTcB) for a single ECG is given by

$$\overline{QTcB} [msec] = \left( \frac{1000}{\overline{RR}} \right)^{1/2} * \overline{QT} [msec].$$

In case of triplicate ECGs at a time point, the respective ECG variable will be averaged over the triplicate ECG measurements at this time point (arithmetic mean). Note that in case of missing values the averaging is simply done for the available values.

## **10. HISTORY TABLE**

Table 10: 1 History table

Version	Date (DD-MMM-YY)	Author	Sections changed	Brief description of change
1	09-FEB-2021	[REDACTED]	None	This is the final TSAP
